8.2 Definitions

8.2.1 Adverse Event

An adverse event (AE) is any untoward medical occurrence in a patient receiving study treatment and which does not necessarily have a causal relationship with this treatment. An AE can be any unfavorable and unintended sign (including an abnormal laboratory finding), symptom, or disease temporally associated with the use of an experimental intervention, whether or not related to the intervention.

- All grade 3 and above AEs will be collected, in addition to any grade ≥ 2 gastritis, hepatic pain, vomiting, and fatigue. The NCI CTCAE v 4.0 will be

utilized to grade AEs and for AE reporting.

- Diagnostic and therapeutic non-invasive and invasive (i.e., surgical) procedures will not be reported as adverse events. However, the medical condition for which the procedure was performed must be reported if it meets the definition of an adverse event unless it is a pre-existing (prior to protocol treatment) condition or a condition entirely unrelated to the study radiotherapy (e.g. cardiac, lung, or bladder procedure).
- Abnormal laboratory values or test results constitute adverse events only if they induce clinical signs or symptoms or require therapy. They are to be captured under the signs, symptoms or diagnoses associated with them.
- When an event recurs after it is resolved, it should be handled as a new AE. However, AEs that occur intermittently can be recorded as one AE.

8.2.2 Serious Adverse Event

An adverse event is considered “serious” if, in the view of either the investigator, it results in any of the following outcomes:

- Death
If death results from (progression of) the disease (cirrhosis or cancer), it is not considered an SAE.
- A life-threatening adverse event
An adverse event is considered ‘life-threatening’ if, in the view of the investigator, its occurrence places the patient or subject at immediate risk of death.
- Inpatient hospitalization or prolongation of existing hospitalization for ≥ 24 hours unless it was related to the disease under study, pre-existing conditions, or an accident, rather than the radiation treatments themselves.
- A congenital anomaly/birth defect

Previously planned (prior to signing the informed consent form) surgeries, hospitalizations, or procedures should not be reported as SAEs unless the underlying medical condition has substantially worsened during the course of the study, unless the investigator deems it definitely unrelated to treatment.

Hospitalization or prolongation of hospitalization without a precipitating clinical AE should not be considered SAEs.

Other adverse events that will be excluded from SAE reporting:

- Death due to cancer or cirrhosis
- Hospitalization secondary to expected cancer or cirrhosis morbidity
- Admission for palliative care or pain management
- Admission for management of biliary obstruction or cholangitis
- Admission for management of deep venous thrombosis or pulmonary embolism
- Planned hospitalizations for surgical procedures
- Accidental injury

Event reporting for oncology protocols, particularly those involving patients with liver disease, can be complicated and confusing to investigators, data managers, and regulatory oversight bodies because patients typically develop numerous complications such as ascites, encephalopathy, peritonitis, GI bleed, blood clot, etc as part of the typical course of cirrhosis and not related to the study therapy.

Therefore, a well-conceived event reporting plan separates background noise as might be seen with any patient with cirrhosis and cancer from study-related events that are relevant to subject safety. In order to achieve this goal, the DSM plan for this study will focus on rapid and specific identification and reporting of the following as SAEs:

- Events which are serious and likely (probably or definitely) related to the investigational component of study therapy (high dose radiotherapy)
- Events occurring at unusual frequency or severity in study subjects compared to

- non-study subjects undergoing similar treatment
- Events that are serious and unexpected

Therefore, we will not report as SAEs events that coincide with a typical cirrhosis or cancer course (ie, expected) unless they are related to the investigational therapy

8.2.3 Expected Adverse Events

An adverse event (AE) is considered “expected” if it is a common side effect related to abdominal radiotherapy. Examples of this include nausea, vomiting, dehydration, fatigue, musculoskeletal discomfort/pain, and dermatitis in the treatment field.

8.2.4 Unexpected Adverse Event

An adverse event (AE) is considered “unexpected” if it is not a common side effect related to abdominal radiotherapy.

8.3 Adverse Event Characteristics

8.3.1 CTCAE Term

(AE description) and grade: The descriptions and grading scales found in the NCI Common Terminology Criteria for Adverse Events (CTCAE) version 4.0 will be utilized for AE reporting. All appropriate treatment areas should have access to a copy of the CTCAE version 4.0. A copy of the CTCAE version 4.0 can be downloaded from the CTEP web site. (<http://ctep.cancer.gov>)

8.3.2 Attribution of the AE

The investigator or co-investigator is responsible for assignment of attribution.

Definite – The AE is *clearly related* to the study treatment

Probable – The AE is *likely related* to the study treatment

Possible – The AE *may be related* to the study treatment Unlikely –

The AE is *doubtfully related* to the study treatment Unrelated – The

AE is *clearly NOT related* to the study treatment

8.4 Serious Adverse Event Reporting Guidelines

- 8.4.1 The Principal Investigator must be notified within 5 business day of study team's knowledge of any event meeting the criteria and definition of a serious adverse event, regardless of attribution, occurring during the study.
- 8.4.2 The investigator must report all events meeting the criteria and definition of a serious adverse event that are unexpected and possibly related (definite, probable or possible) to study treatment to the local IRB within 7 days of study team's knowledge.
- 8.4.3 All Serious Adverse that are unexpected and possibly related (definite, probable or possible) to study treatment will be reported to the IRB using CTO Serious Adverse Event form.

8.5 Routine Reporting

All other adverse events- such as those that are expected, or are unlikely or definitely not related to the study participation- are to be reported annually as part of regular data submission.

8.6 Reporting of Unanticipated Problems

There are types of incidents, experiences and outcomes that occur during the conduct of human subjects research that represent unanticipated problems but are not considered adverse events. For example, some unanticipated problems involve social or economic harm instead of the physical or psychological harm associated with adverse events. In other cases, unanticipated problems place subjects or others at increased risk of harm, but no harm occurs.

Upon becoming aware of any incident, experience, or outcome (not related to an adverse event) that may represent an unanticipated problem, the investigator should assess whether the incident, experience, or outcome represents an unanticipated problem. The incident, experience or outcomes is considered unanticipated if it meets all of the following criteria:

1. Unexpected (in terms of nature, severity, or frequency);
2. Related or possibly related to participation in the research; and
3. Suggests that the research places subjects or others at a greater risk of harm than was previously known or recognized.

If the investigator determines that the incident, experience, or outcome represents an unanticipated problem, the investigator must report it to the IRB within 14 calendar days of the study team becoming aware of the problem.

8.7 Stopping Rules

[figure not shown]
There are separate stopping rules for efficacy and toxicity. The goal is to stop the trial if there is evidence that the true rate of toxicity (defined in section 8.2) exceeds 10% OR the true rate of local progression within 6 months exceeds 30%. The efficacy rule will be evaluated 6 months after the 10th patient is enrolled. Given expected enrollment of about 1 patient per month, this evaluation will occur when approximately 16 patients have been enrolled. The trial will be stopped if 5 or more of the 10 patients with 6 month follow-up experienced disease-related progression within 6 months of treatment. When the true probability of progression within 6 months is 10, 30 or 50%, the probability of stopping is 1, 15 and 62%, respectively.

The toxicity rule will be evaluated after 15 patients are evaluable for toxicity which will occur 3 months after enrollment of the 15th patient. If 4 or more patients experience unacceptable toxicity, defined as radiation induced liver disease, the trial will be halted. When the true probability of toxicity is 5, 10 or 30%, the probability of stopping is <1, 6 and 70%, respectively.

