5.0 TREATMENT PLAN

5.1 Treatment Dosage and Administration

Protocol treatment must start within 30 business days of enrollment to the study.

- 5.1.1 Global and regional assessment of liver function
 - 5.1.1.1 Global functional assessment with indocyanine green (ICG) clearance Preparation and administration of indocyanine green will be as per package insert by trained personnel in the Michigan Clinical Research Unit (MCRU). In some patients, indocyanine green will not be used, in favor of ALBI score.

5.1.1.1.1 Evaluations with ICG or ALBI will occur within 4 weeks prior to the start of RT, at approximately 4-6 weeks after the completion of the first 3/5 of planned treatments, and approximately 1-3 months after RT is completed.

5.1.1.1.2 For patients scheduled to have ICG testing for other reasons (including prior or subsequent enrollment in this or other protocols), every effort will be made to use results for both purposes, to avoid duplication, including extending windows by an extra 4 weeks in each direction.

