6.3 Follow-Up Procedures

Patients will be evaluated approximately 1 month after completion of therapy and then at approximately 3-6 month intervals until 2 years. Evaluation will include H&P, laboratories (CBC, comprehensive metabolic panel, INR, AFP if elevated at diagnosis), and liver imaging (beginning 3 months after treatment). QOL assessments will be obtained at the same intervals for 1 year. ICG or ALBI will be assessed approximately 1 and 3 months after completion of therapy. Blood and urine (when patient is able to provide) will be collected at approximately 1 and 3 months after completion of therapy. MRI will be assessed approximately 1 month after completion of therapy. This follow up schedule will adhere to standard of care clinical follow up. Therefore, missed visits and visits that diverge from this regimen will not be considered protocol deviations. MRI and ICG must be performed at the University of Michigan. However, if patients are not able to travel for all other follow up evaluations and procedures, they may have these performed by a local physician and records obtained by the study team. If patients are concurrently or previously enrolled in another research study which requires similar testing, all efforts will be made to avoid unnecessary repeat testing.

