6.4 Time and Events Table

	Pre-Rx Eval ¹	Initial RT Phase	Active Treatment	
			Evaluation Period Approximately 4-6 Weeks after Initial RT Phase	Final RT phase ⁵
History, Physical Exam, Performance Status, QOL⁸	X	PS	QOL	PS
Weight	X	Once	X	Once
CBC/Platelets	X		X	
AST, ALT, Alk Phos, Bilirubin	X		X	
BUN/Creatinine	X		X	
INR	X		X	
AFP (for HCC)	X		X	
Toxicity Notation	X	Once		Once
MELD/CTP assessment	X		X	
IC-Green⁶	X		X ⁴	
Simulation	X		X	
Perfusion MRI⁹	X		X	
Tumor biopsy⁷	X			
Diagnostic CT or MRI of liver	X ²			
Chest imaging with x-ray or CT	X ³			
Plasma and serum	X		X	
Radiation Treatment (RT)		X		X

¹ From 30 days prior to signed ICF, through treatment start.

² From 90 days prior to signed ICF, through treatment start.

³ Within 1 year prior to enrollment

⁴ If a patient does not initially qualify for the final RT phase, he/she will undergo repeat IC-Green in approximately 4 weeks as a second attempt.

⁵ Patients who do not qualify for the final RT phase will not undergo any of the treatment or testing associated with that phase. The final day of the initial RT phase will be counted as the last day of treatment, and the follow up calendar will be initiated.

⁶ For patients indicated to receive IC-Green from the treating physician. If the patient was previously enrolled on any trial utilizing IC-Green (including this one), then an evaluation of IC-Green retention performed for the other trial may be used as the pre-treatment assessment for this enrollment, as long as it is within 30 days prior to initiation of this new course of RT.

⁷ Biopsy only performed if patient consents

⁸ QOL will consist of the Functional Assessment of Cancer Therapy-Hepatobiliary (FACT-HEP) version 4. As patients can be seen in a variety of clinics, and occasionally do not follow a standard clinic schedule, missed QOLs will not be reported as a protocol deviation.

⁹ Description of Perfusion MRI protocol in the appendix.

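### Both stopping looks in Section 8.7 are dated from enrollment, not from radiotherapy, so on those dates the latest patients need not be fully observed and the stated stopping probabilities are somewhat too high

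*Combined protocol and SAP*

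**What the plan says.** Section 8.7 sets one look for each rule and dates both from enrollment.

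- **Efficacy look:** "The efficacy rule will be evaluated 6 months after the 10th patient is enrolled". **Rule:** "The trial will be stopped if 5 or more of the 10 patients with 6 month follow-up experienced disease-related progression within 6 months of treatment". **Forecast:** "Given expected enrollment of about 1 patient per month, this evaluation will occur when approximately 16 patients have been enrolled". At true rates of 10, 30 and 50%, "the probability of stopping is 1, 15 and 62%, respectively".
- **Toxicity look:** once 15 patients are evaluable, "which will occur 3 months after enrollment of the 15th patient". The trial halts at 4 or more patients with radiation-induced liver disease. The stated stopping probabilities are below 1, 6 and 70% at true rates of 5, 10 and 30%. No time window is attached to the event.

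Elsewhere in the document:

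- Section 5.1: "Protocol treatment must start within 30 business days of enrollment to the study".
- Section 7.1.5 runs progression-free survival from the start of treatment.
- Section 7.1.1 makes every patient evaluable for toxicity from the first fraction, with no minimum observation time.
- Sections 11.1 and 11.3 judge the primary toxicity endpoint, a Child-Pugh increase of 2 or more, over six months from radiotherapy.

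**The concern.** The date of the efficacy look and the event it counts have different time origins. The forecast of 16 enrolled is exactly 10 plus six months at one per month, so no time was allowed between enrollment and treatment. The toxicity look comes three months after the 15th enrollment. That cannot cover a six-month window for the last patients, even if each starts radiotherapy on the day of enrollment.

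If the looks are held on the stated dates, the latest patients have had less time to show an event. Shorter observation can only lower the count, so each rule is less likely to stop the trial than its stated probability suggests. These are the protocol's numerical trial-level stopping rules, and the monitoring bodies would rely on the stated figures.

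**Working it through.** **1. Reproduce the stated figures.** These are exact binomial tails with every patient fully observed.

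- Efficacy, P(X ≥ 5), n = 10: 0.2%, 15.0% and 62.3% at 10, 30 and 50%. Stated: 1, 15 and 62%. The first is 0.16% exactly; the others agree.
- Toxicity, P(X ≥ 4), n = 15: 0.5%, 5.6% and 70.3% at 5, 10 and 30%. Stated: below 1, 6 and 70%. All agree.

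**2. Inputs.** Look time L is 6 months (efficacy) or 3 months (toxicity) after the last counted enrollment (8.7). Accrual is one per month (8.7). Maximum start delay is 30 business days = 6 weeks = 1.38 months (5.1). Assumed: even spacing of enrollments, the same delay d for all patients, and an event time that is either constant-hazard or uniform over the window w.

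**3. Formula.** Patient k of n has been observed from the start of radiotherapy for t(k) = min(w, L − d + (n − k) × 1 month). The chance that the event has occurred by the look is 1 − (1 − p)^(t/w) under constant hazard, or p × t/w under uniform onset. The chance of stopping is the upper tail of the sum of these unequal Bernoulli variables.

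**4. Efficacy, w = 6 months from start, d = 1.38.** Patients 1-8 are complete. Patient 9 has 6 − 1.38 + 1 = 5.62 months and patient 10 has 4.62. At p = 0.50 under constant hazard, their event probabilities are 1 − 0.5^(5.62/6) = 0.478 and 1 − 0.5^(4.62/6) = 0.414.

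| True rate | Fully observed | Constant hazard | Uniform |
|---|---|---|---|
| 30% | 15.0% | 13.7% | 13.5% |
| 50% | 62.3% | 59.6% | 58.7% |

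**5. Toxicity, true rate 30%.** Section 8.7 gives no window, so each row assumes one.

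| Assumed window | Delay | Patients short | Constant hazard | Uniform |
|---|---|---|---|---|
| Full observation | – | 0 of 15 | 70.3% | 70.3% |
| 3 months from start | 6 weeks | 2 | 67.2% | 66.8% |
| 6 months from start | none | 3 | 64.9% | 64.3% |
| 6 months from start | 6 weeks | 5 | 58.9% | 57.8% |
| 6 months after completion (8-week course assumed: 26 + 8 = 34 weeks from start) | 3 weeks | 6 | 57% | 55% |
| As above | 6 weeks | 7 | 53% | 51% |

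**6. Which feature causes the loss.** Take the six-month window from start with a 6-week delay, under constant hazard. The total loss is 70.3 − 58.9 = 11.4 points. The window mismatch alone costs 70.3 − 64.9 = 5.4 points with no delay. If the delay is introduced first (70.3 to 67.2), the longer window then costs 67.2 − 58.9 = 8.3 points. So the three- versus six-month mismatch accounts for roughly half to three-quarters of the loss, depending on the order, and the enrollment clock for the rest.

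**7. When full observation would be reached.** At the maximum delay, the 10th patient completes six months from start at 6 + 1.38 = 7.4 months after enrollment, with about 17 enrolled.

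**The case against.** The best defence is that the conditions govern and the dates are only forecasts. The efficacy rule refers to ten patients with six months of follow-up, and the toxicity rule acts once 15 are evaluable. Read that way, the efficacy probabilities hold as stated. This stands as a possible reading, but it does not rescue the text: the efficacy look date and the 16 enrolled would then be wrong. For toxicity, being evaluable requires only a first fraction.

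Several stronger conclusions are tempting, and the documents do not support them.

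- *The toxicity rule loses a third or more of its power.* That needs the six-month Child-Pugh window, run from completion of treatment and with faster accrual, to be imposed on a rule whose event is radiation-induced liver disease. Section 11.3 lists that event separately, and Section 8.7 gives it no window. What can be shown is a missing window.
- *The treatment break shortens follow-up.* It matters only if the clock runs from completion. Section 7.1.5 runs progression from the start.
- *The 10th patient may have no post-treatment imaging by the look.* Section 6.3 starts routine liver imaging three months after treatment, but it also schedules an MRI about one month after therapy.
- *The plan counts unobserved patients as event-free.* No passage says so. It follows only if the looks are held on the stated dates with all 10 or 15 in the denominator.

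Two further points stand. Six weeks is a ceiling, not the expected delay. Section 12 provides quarterly committee review and reporting to an independent board, so the formal looks are not the only protection. Section 1.1.4 also mentions an analysis of the first 20 evaluable patients. If that means this study, both looks may already have passed.

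**Conclusion.** The point holds at modest size. The dates in Section 8.7 do not guarantee the full observation on which its probabilities rest. From the start of radiotherapy, at one patient per month and the maximum delay, the efficacy loss is 3-4 points at a 50% rate and about 1.5 points at 30%.

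For toxicity at a 30% rate the loss depends on a window that the rule does not state. It is about 3 points for an assumed three-month window and 5-6 points for a six-month window with no delay. It is 11-13 points for six months with the maximum delay, and about 13-19 points if the window ends six months after completion of an assumed 8-week course.

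The results rest on even accrual, a common delay and the two onset models. The 20 patients per year in Section 11.2 would enlarge the losses: with the six-month window from start and maximum delay, toxicity stopping falls to about 50-52%. That accrual conflict is a separate matter. On none of these readings does the chance of stopping exceed the fully observed value.

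**What to change.** Amend Section 8.7 as follows.

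1. State one time origin, tied to radiotherapy, and one window for each rule. Reconcile the toxicity event and its window with Section 11. Which clinical definition applies is for the investigators.
2. Make the final efficacy determination when the 10th treated patient has six months from start of treatment with a post-treatment tumor assessment. Make the final toxicity determination when the 15th treated patient completes the stated window.
3. Count events cumulatively among those first 10 and 15 treated patients, so that the 5th progression or the 4th toxicity triggers the rule at once. The count crosses the boundary early only if the final count would reach it, so the binomial probabilities in Section 8.7 are unchanged.
4. Delete "which will occur 3 months after enrollment of the 15th patient" and restate the number expected to be enrolled at each look.
5. If the looks have already taken place, record how long each counted patient had been observed.

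**Cost.** This is a wording change. A stop is not delayed. At the maximum delay and one patient per month, the decision to continue moves about 1.4 months later for efficacy (about 17 enrolled, not 16). For toxicity with a six-month window it moves from 3 months after the 15th enrollment to 6 months (no delay), 6 + 1.38 = 7.4 months (maximum delay), or about 9.2 months (window from completion, 8-week course). That is roughly 3-6 months later, with about 3-6 more patients enrolled meanwhile.

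### Section 8.7: the efficacy rule's stated 1% chance of stopping at a true 10% progression rate should read <1% (exact 0.16%); the 15% and 62% are correct

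*Combined protocol and SAP*

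**What the plan says.** Section 8.7 of the combined protocol and SAP gives separate rules for efficacy and toxicity. The efficacy rule is meant to stop the trial on evidence that "the true rate of local progression within 6 months exceeds 30" percent. It has one look: "The efficacy rule will be evaluated 6 months after the 10th patient is enrolled". The boundary is given in words: "The trial will be stopped if 5 or more of the 10 patients with 6 month follow-up experienced disease-related progression within 6 months of treatment".

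The operating characteristics follow. The scenarios are introduced by "When the true probability of progression within 6 months is 10, 30 or 50" percent, and for these "the probability of stopping is 1, 15 and 62%, respectively".

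The toxicity rule has the same structure. "The toxicity rule will be evaluated after 15 patients are evaluable for toxicity", and "If 4 or more patients experience unacceptable toxicity, defined as radiation induced liver disease, the trial will be halted". At true toxicity rates of 5, 10 and 30%, its stopping probabilities are given as below 1% (printed with a less-than sign), 6% and 70%.

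**The concern.** A single look with a fixed boundary has operating characteristics that follow exactly from the binomial distribution, so each of the three stated figures can be checked. Two agree with the written rule and one does not.

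The figure that fails is the false-stop probability: the chance of halting the trial when the true 6-month progression rate is 10%, well under the 30% that the rule guards against. Those who approve or oversee the trial rely on that number to judge how safely the rule lets a good treatment continue, so it should be right even when the error is small.

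**Working it through.** **Inputs, all from section 8.7.** Patients assessed n = 10; stop if X ≥ 5; one look; true 6-month progression rates p = 0.10, 0.30 and 0.50; stated stopping probabilities 1%, 15% and 62%.

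**Formula.** With X ~ Binomial(10, p), P(stop) = Σ C(10, k) p^k (1 − p)^(10 − k), summed over k = 5 to 10.

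**The two figures that reproduce.**

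- p = 0.50: (252 + 210 + 120 + 45 + 10 + 1) / 1024 = 638 / 1024 = 0.6230. Stated 62%.
- p = 0.30: 0.10292 + 0.03676 + 0.00900 + 0.00145 + 0.00014 + 0.00001 = 0.1503 (terms rounded). Stated 15%.

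**The figure that does not.** At p = 0.10:

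- k = 5: 252 × 0.1^5 × 0.9^5 = 0.001488
- k = 6: 210 × 0.1^6 × 0.9^4 = 0.000138
- k = 7: 120 × 0.1^7 × 0.9^3 = 0.000009
- k = 8 to 10: together less than 0.000001
- Sum: 0.001635, or 0.16%. Stated 1%.

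| True rate | Stated | Exact, 5 or more of 10 | Stated − exact |
|---|---|---|---|
| 10% | 1% | 0.16% | +0.84 points |
| 30% | 15% | 15.03% | −0.03 points |
| 50% | 62% | 62.30% | −0.30 points |

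**Does a rounding habit explain the 1%?** Rounding to the nearest whole percent gives 0, 15 and 62. Rounding every figure up gives 1, 16 and 63. Neither gives the stated trio.

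**Does an approximation explain it?** At p = 0.10 and a boundary of 5, the normal approximation gives about 0.01% with continuity correction and less without. The Poisson approximation gives 0.37%. Neither gives 1%.

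**Does another sample size or boundary explain it?** Samples of 9, 10, 11, 12 and 16 were tried with boundaries from 3 to 7. No pair gives 1, 15 and 62% together.

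**The neighbouring rule.** For 4 or more of 15, the exact probabilities at true toxicity rates of 5, 10 and 30% are 0.55%, 5.56% and 70.3%. They match the stated figures of below 1%, 6% and 70%. There a value of 0.55%, which would round to 1%, is shown as less than 1%. By that convention 0.16% should be shown the same way.

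**The case against.** The strongest reply is that this is immaterial. The absolute error is 0.84 percentage points. A ratio of about six (1 / 0.16) sounds large only because both numbers are close to zero. Under either figure a false stop at a 10% rate is very unlikely, and the written rule does slightly better there than the plan claims. A tolerance of 2 points, reasonable for a power figure, would pass all three numbers. The look was expected at about 16 enrolled patients, and section 1.1.4 mentions an analysis of the first 20 evaluable patients. If that refers to this trial, the look has already passed and the correction is editorial. All of this stands as a limit on importance. It does not make the 1% right: a 2-point tolerance is too coarse for a probability of 0.16%, since it would accept anything from 0 to about 2.2%.

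A reader might also go further and infer that the three figures come from different rules, or that a boundary of 4 was intended, because 4 or more of 10 gives 1.28% at a 10% rate. The documents do not support this. The boundary is written as 5, and a boundary of 4 would give 35.0% and 82.8% at the other two rates, far from the stated 15% and 62%. The match rests on one single-digit number near zero, and other routes reach it too: the written boundary of 5 gives 0.99% at a true rate of 15%. A dropped less-than sign, or rounding this one figure up to the smallest whole percent, is a simpler explanation. The documents confirm none of these origins, and the correction does not depend on which is true.

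**Conclusion.** The point holds as a minor correction of one figure. For the rule as written, the stopping probability at a true 10% progression rate is 0.16%, so the stated 1% overstates the false-stop chance by 0.84 points. The 15% and 62% are correct and, with the wording of the rule, identify the boundary as 5. This is not an inconsistent stopping rule.

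The calculation assumes that exactly 10 patients are assessed at one look, as section 8.7 describes, and that their outcomes are independent with a common progression probability. The plan's own 15% and 62% follow from the same assumptions.

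**What to change.** In section 8.7, leave the boundary at 5 or more of 10 and restate the stopping probabilities at true rates of 10, 30 and 50% as <1, 15 and 62%, which matches the style of the toxicity rule. Printing 0.2, 15 and 62% would serve equally well. The cost is one number in one sentence, with no change to the boundary, the look, the sample size or the conduct of the trial.
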